2.1 Objectives

2.1.1 Primary Objective

• The primary objective is to assess the effect of a GnRH receptor antagonist (degarelix) on the risk of occurrence of MACEs (a composite of death due to any cause, non-fatal myocardial infarction or non-fatal stroke) as compared to a GnRH receptor agonist (leuprolide) in patients with prostate cancer and concomitant CVD

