**Statistical Analyses**

*Primary Analysis*

The primary endpoint, the time from randomization to the first confirmed occurrence of the composite MACE endpoint in the two treatment groups, will be analyzed based on the Kaplan-Meier estimator of the survival function and the log-rank test stratified for age group and region.

The null hypothesis of equal hazard functions between the two treatment groups, will be rejected if the test statistics exceed the critical level for a two-sided hypothesis test with a Type I error level of 5%.

Conclusions on significance of the primary endpoint analysis will be based on the Full Analysis Set (FAS) censoring patients at the time of treatment discontinuation, initiation of prohibited therapies related to hormonal treatment, lost to follow-up/withdrawal from the trial or Day 336, whichever occurs first.

*Secondary Analyses*

If the primary analysis is significant at the two-sided Type I error-level of 5% the testing of the key secondary endpoints will proceed as described below.

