### 9.1 Determination of Sample Size

The primary objective is to assess the effect of degarelix on the risk of MACEs (a composite of death due to any cause, non-fatal myocardial infarction or non-fatal stroke) occurring during a 1-year period as compared to treatment with a GnRH receptor agonist (leuprolide) in patients with prostate cancer and pre-existing CVD.

As suggested by a post-hoc analysis of degarelix safety data the 1-year event rates for a CV event or death due to any cause are 5.3% and 12.1% for degarelix and leuprolide, respectively, in the global patient population with prior CVD. This would correspond to an unadjusted treatment-related hazard ratio of 0.42. In comparison, the adjusted hazard ratio is 0.39 (95% confidence interval = [0.21; 0.71]). Furthermore, based upon the re-assessment of the potential CV events captured in the degarelix safety data by an independent cardiologist, the 1-year event rates for CV event or death due to any cause are 4.8% and 9.3% for degarelix and leuprolide respectively. This corresponds to an unadjusted hazard ratio of 0.50. In comparison, the adjusted hazard ratio is 0.48 (95% confidence interval [0.23; 0.87]). Accounting for the uncertainty in the post-hoc analysis of the global pooled data and the re-assessment of the potential CV events by a single independent cardiologist, the 1-year event rates for sample size calculations are set to 5.1% and 10.2% for degarelix and leuprolide, respectively. This corresponds to a hypothesized hazard ratio of 0.49.

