2.1.2 Secondary Objectives

CV and Death Related Objectives

- To assess the rate of specific MACEs (individual components of the composite MACE endpoint), i.e. myocardial infarction (fatal, non-fatal), stroke (fatal, non-fatal), in patients randomized to degarelix versus leuprolide
- To assess the rate of unstable angina requiring hospitalization (fatal, non-fatal), in patients randomized to degarelix versus leuprolide
- To assess the risk of death due to any cause in patients randomized to degarelix versus leuprolide
- To assess the rate of cardiovascular (CV)-related death in patients randomized to degarelix versus leuprolide

Prostate Cancer-Related Objectives

- To monitor testosterone levels at Day 28, 168 and 336 in the degarelix and leuprolide treatment groups
- To evaluate the progression-free survival (PFS) failure rates (defined as either death, radiographic disease progression^a, introduction of additional therapy related to prostate cancer^b or prostate-specific antigen [PSA] failure^c, whichever is first) in the degarelix and leuprolide treatment groups
 - a. One or more new metastatic skeletal lesions observed on bone scan; one or more new metastatic extraskeletal lesions at least 1.5 cm in greatest dimension visible on computed tomography or magnetic resonance imaging (MRI) scan as confirmed by the Investigator.
 - b. Additional therapy includes radiation, anti-androgens (except for initial symptomatic flare protection) and second-line treatment.
 - c. PSA failure is defined as an increase in serum PSA of 50%, and at least 5 ng/mL, compared to nadir, measured on two consecutive occasions at least 2 weeks a part.
- To compare the effects of degarelix with leuprolide with regards to local urinary tract and prostate cancer-related symptoms with the International Prostate Symptom Score (IPSS) questionnaire

Health Economics and Patient Reported Outcome (PRO) Objectives

• To compare the effects of degarelix with leuprolide with regards to healthcare resource use

Date: 24 Feb 2021 E-Statistical Analysis Plan-19595; Ver.7.0 Supersedes: 6.0 Page 11 of 51

- To compare the effects of degarelix with leuprolide with regards to health status through the EuroQol Group 5 Dimensions Questionnaire (EQ-5D-5L)
- To compare the effects of degarelix with leuprolide with regards to functional capacity and Quality of Life (QoL) through the Duke Activity Status Index (DASI)

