9.1 General Considerations

The analysis of efficacy will be performed for the FAS (unless otherwise specified). For the purpose of this CV outcome study, patients prematurely discontinuing from treatment will be followed-up for the occurrence of MACE events based on monthly telephone interviews. Unless otherwise stated, time to event endpoints will be censored at the time of treatment discontinuation, initiation of prohibited therapies related to hormonal therapy, lost to follow-up/withdrawal from the study or day 336, whichever occurs first. Initiation of prohibited therapy related to hormonal therapy includes the following:

- Surgical castration or other hormonal manipulation in addition to the IMPs
- Anti-androgens for combined androgen blockade (anti-androgen use for initial flare protection is allowed for a maximum period of up to 28 days after randomization)
- Estrogens
- Megestrol acetate
- Ketoconazole
- Abiraterone
- Enzalutamide
- Any additional hormonal therapy initiated as a combination therapy with the IMP

The associated ATC and MedDRA codes for the above prohibited therapies are provided in Table 11 and Table 12. Hypothesis tests will be two-sided at a significance level of 5% and missing data will not be imputed. 95% confidence limits and the associated p-values will be presented for estimates of the treatment effect comparing degarelix to leuprolide for all regression analyses.

For the purposes of	this trial,		
_			
			•

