9.2.2 Sensitivity Analyses

9.2.2.1 Sensitivity Analysis: Time from randomization to the first confirmed (adjudicated) occurrence of non-fatal myocardial infarction, non-fatal stroke, non-fatal unstable angina requiring hospitalization, or all-cause death

Time from randomization to the first confirmed (adjudicated) occurrence of non-fatal myocardial infarction, non-fatal stroke, non-fatal unstable angina requiring hospitalization, or all-cause death is defined similarly as the primary endpoint with the addition of cardiovascular events unstable angina requiring hospitalization. Also, the endpoint will be analyzed as for the primary endpoint.

9.2.2.2 Sensitivity Analysis: Time to first confirmed occurrence of a MACE related adverse event (MI SMQ (broad); Central nervous system hemorrhages and cerebrovascular conditions SMQ (broad); all-cause death)

Time to first confirmed occurrence of a MACE related adverse event is defined as for the primary endpoint with events being; any adverse event within the broad SMQ term 'myocardial infarction', any adverse event within broad SMQ term 'Central nervous system hemorrhages and cerebrovascular conditions' or all-cause death. Also, the endpoint will be analyzed as for the primary endpoint.

9.2.2.3 Sensitivity Analysis: Total occurrence of (adjudicated) myocardial infarction, stroke, and all-cause death

Total occurrence of myocardial infarction (MI), stroke and all-cause death is defined as the total number of events (MI, stroke or death) occurring over the duration of the trial.

The endpoint will be compared between treatment groups using a negative binomial model. The estimated treatment difference with a 95% confidence interval will be presented.

9.2.2.4 Sensitivity Analysis pertaining to treatment discontinuation or initiation of prohibited therapies related to hormonal therapy

For the purposes of this sensitivity analysis, patients will NOT be censored at the time of treatment discontinuation or initiation of prohibited therapies related to hormonal therapy. Rather, information pertaining to all observed occurrences of the first adjudicated MACE event in patients randomized in the study will be used. Patients will be censored at lost to follow-up/withdrawal from study or day 336, whichever occurs first.

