Time from randomization to the first adjudicated occurrence of the individual components of the MACE composite endpoint is defined as the number of days from randomization to the first adjudicated myocardial infarction/stroke. The occurrence of the components of the MACE composite endpoint will be adjudicated by the external independent CEC Committee. In order to correctly assess the treatment effect associated with degarelix with respect to the time to individual components of the MACE composite endpoint, it is necessary to account for the competing risk, death due to other causes. The above components of the MACE composite endpoint will be analyzed separately. The log-rank test stratified by age-group and region will be used to examine the null hypothesis of equal cumulative cause specific hazard functions. The p-value of the two-sided log rank test with significance level of 5% will be presented along with the plots of the estimated cumulative cause specific hazard functions for both treatments obtained from the Nelson-Aalen estimator, stratified by age group and region.

TLF Table: Secondary Endpoint: Time to First Adjudicated Myocardial Infarction - FAS

TLF Figure: Cumulative Cause Specific Hazard Function for Time to First Adjudicated Myocardial Infarction – FAS

TLF Table: Secondary Endpoint: Time to First Adjudicated Stroke - FAS

TLF Figure: Cumulative Cause Specific Hazard Function for Time to First Adjudicated Stroke – FAS

Page 28 of 51

9.3.3 Time from randomization to the first confirmed (adjudicated) unstable angina requiring hospitalization

Time from randomization to the first adjudicated occurrence of unstable angina requiring hospitalization will be analyzed in the same manner as the individual components of the MACE primary endpoint, specified in Section 9.3.2.

TLF Table: Secondary Endpoint: Time to First Adjudicated Unstable Angina Requiring Hospitalization – FAS

TLF Figure: Cumulative Cause Specific Hazard Function for Time to First Adjudicated Unstable Angina Requiring Hospitalization – FAS

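### A fatal MI or stroke reaches the primary composite only through the death, so one whose death falls after censoring may give no primary event

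*SAP*

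**What the plan says.** - **Primary composite.** SAP 2.1.1 gives "a composite of death due to any cause, non-fatal myocardial infarction or non-fatal stroke". Protocol 2.1.1 and 9.1 agree.
- **Components.** The next objective, SAP 2.1.2, describes the individual components of that composite without the restriction: "i.e. myocardial infarction (fatal, non-fatal), stroke (fatal, non-fatal), in patients randomized to degarelix versus leuprolide". SAP 9.3.2 gives the time to each component, which "is defined as the number of days from randomization to the first adjudicated myocardial infarction/stroke".
- **Censoring.** SAP 9.1 sets the default: "time to event endpoints will be censored at the time of treatment discontinuation, initiation of prohibited therapies related to hormonal therapy", or loss/withdrawal, or Day 336, whichever is earliest. Protocol 9.6.1 and the synopsis state the same rule for the primary test.
- **First key secondary.** SAP 9.3.1 makes it the same as the primary endpoint except that only CV deaths count.
- **Sensitivity analyses of the primary endpoint.** In SAP 9.2.2.4, "patients will NOT be censored at the time of treatment discontinuation or initiation of prohibited therapies related to hormonal therapy", while the Day 336 limit stays. SAP 9.2.2.3 counts all MIs, strokes and deaths with no non-fatal qualifier.
- **Success.** SAP 9.2.1 rests it on the stratified log-rank test of the primary analysis.
- **Adjudication.** Protocol 7.1.1 places the full process in a separate CEC charter.

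**The concern.** Without censoring, restricting MI and stroke to non-fatal ones does no harm: every fatal one is picked up by all-cause death, only on a later date. With censoring between the event and the death, that no longer holds. The MI is excluded because it is not non-fatal, and the death is excluded because it falls after the censoring date.

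A patient could then have an MI in the third key secondary endpoint and no event in the primary composite, which is meant to contain it. The events at risk are the most severe ones. With few events in the trial, a definition that can drop even one deserves to be closed.

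**Working it through.** **1. Following the rules through.** The days below are invented to show how the definitions act. Day 84 is a dosing day in both arms (Protocol Table 2). The MI endpoint column assumes that the event is dated on the day of the MI.

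| Path | Primary and first key secondary | MI endpoint | Primary under 9.2.2.4 | Primary after the fix |
|---|---|---|---|---|
| A. MI Day 100 labelled fatal, no stop recorded, death Day 110 | Event Day 110 | Event Day 100 | Event Day 110 | Event Day 100 |
| B. MI Day 100 labelled fatal, stop dated Day 105, death Day 110 | None (censored Day 105) | Event Day 100 | Event Day 110 | Event Day 100 |
| C. MI Day 330 labelled fatal, death Day 340 | None (censored Day 336) | Event Day 330 | None | Event Day 330 |
| D. As B, but labelled a non-fatal MI followed by death | Event Day 100 | Event Day 100 | Event Day 100 | Event Day 100 |
| E. As B, but the stop dated at the last injection, Day 84 | None (censored Day 84) | None | Event Day 110 | None |

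Paths B and C are the gap. Start of prohibited hormonal treatment acts like the stop in B. Path C is not recovered by 9.2.2.4. That analysis also belongs to the primary endpoint only, so the first key secondary has no counterpart.

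**2. The plan's own figures, reproduced.** Inputs from SAP 3.2 to 3.2.3: 1-year rates 5.1% and 10.2%, two-sided 5%, power 80%, 1:1 allocation.

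- HR = ln(1 − 0.051)/ln(1 − 0.102) = 0.0523/0.1076 = 0.4866.
- Schoenfeld events = 4(1.960 + 0.842)²/(ln 0.4866)² = 60.5, so 61. This matches the SAP.
- With the futility bound Z > 0.7 at 33 of 66 events (bivariate normal, correlation √0.5), power is 80.4%. This matches the stated 80%.

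**3. What lost events would cost in power.** The number lost is an assumption.

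| Events lost of 66 | 0 | 1 | 3 | 5 | 10 |
|---|---|---|---|---|---|
| Power | 80.4% | 79.8% | 78.6% | 77.3% | 73.8% |

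Without the futility look, at the assumed HR, power is 27.0% at 14 events, 25.4% at 13 and 28.6% at 15. Thirteen and 15 are both shown because the documents do not say whether an affected patient would be among the 14. The effect on power is small either way.

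**4. Fragility at 14 events, as illustration only.** With similar risk sets, Z ≈ (a − b)/√(a + b).

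- 11 v 3: 8/√14 = 2.14, p = 0.033. Without one leuprolide event, 10 v 3: 7/√13 = 1.94, p = 0.052.
- 12 v 2: 10/√14 = 2.67. Without one, 11 v 2: 9/√13 = 2.50, still significant.
- 10 v 4: 6/√14 = 1.60, not significant to begin with.

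One event can matter at one particular split and not at its neighbours. The documents give no split by arm.

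**The case against.** The strongest reply is that the definitions do not contradict each other. A composite with all-cause death contains every fatal MI and stroke, and the loss needs two conditions that the documents do not establish.

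- **Labelling.** The event must be called fatal despite the delay to death. The exploratory endpoint (SAP 9.4.1) follows patients from a first non-fatal MACE to a second, which suits reading an MI survived for some days as non-fatal (path D). The rule may be in the CEC charter, which is not part of these documents. This stands, and it makes the gap conditional.
- **Stop date.** A stop must fall between event and death. SAP section 4 ties going off drug to the last injection. If that is the censoring date, the MI endpoint loses the event too and the fix recovers nothing on that path (path E). Some text in SAP 9.1 is missing from the public copy and may define the date. Protocol 4.4 also encourages keeping patients in the trial after a CV event, which makes path A more likely. All of this stands, but path C does not depend on the stop date.
- **Existing cover.** SAP 9.2.2.4 recovers path B. SAP 9.2.2.3 drops the non-fatal qualifier, and 9.2.2.2 counts MI and cerebrovascular adverse events without it, so either may capture path C. This stands in part: none of these decides success.

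A reader might also infer that a sizeable share of fatal events is lost, or that the loss favours one arm because dosing is every 28 days against every 84. The documents support neither. They give no case fatality, no delay to death and no stop frequency, so any percentage would mostly return the assumed chance of a stop. An imbalance by arm would need an assumed rule for dating the stop. Nor do they say that components are timed from symptom onset; SAP 9.3.2 refers only to the adjudicated event.

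**Conclusion.** The concern holds as a gap between the endpoint definition and the censoring rule, in the current text of both documents. If the CEC labels an on-treatment MI or stroke as fatal and the death falls after a recorded stop or after Day 336, the primary analysis and the first key secondary record nothing, while the component endpoint can record an event.

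Its frequency cannot be computed from the documents and is probably low. At the planned 66 events, one lost event costs about 0.6 points of power (80.4% to 79.8%). The planned design was also event-driven, so longer accrual could have made up the number. At termination one event is 7% of the data. The issue is therefore coherence and possible bias in the analysis that decides success, not sample size. The conclusion rests on a literal reading of the non-fatal qualifier and on a stop, where there is one, dated after the MI or stroke.

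**What to change.** Define the primary composite as the first of all-cause death, any adjudicated MI or any adjudicated stroke, fatal or non-fatal, with MI and stroke dated at the adjudicated event. Define the first key secondary in the same way with CV death. This agrees with SAP 2.1.2, 9.2.2.3 and 9.3.2, and with the table title under SAP 9.3.1, which already omits the non-fatal qualifier. State in SAP 9.1, or point to where it is stated, which date counts as the treatment stop, because path E depends on it.

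The cost is wording in the SAP and the matching protocol sections. No new data are needed, since MI and stroke dates are already required for the component endpoints, and each patient still contributes at most one first event. Some fatal events will be dated slightly earlier. SAP version 7.0 postdates termination and treatment is open-label, so the change should be documented as made without reference to results by arm. If the sponsor prefers not to redefine the endpoint at this stage, the minimum is a sentence giving the fatal/non-fatal rule and event date, or citing the charter for them. That makes the gap visible but does not close it.

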2.1.2 Secondary Objectives

CV and Death Related Objectives

- To assess the rate of specific MACEs (individual components of the composite MACE endpoint), i.e. myocardial infarction (fatal, non-fatal), stroke (fatal, non-fatal), in patients randomized to degarelix versus leuprolide
- To assess the rate of unstable angina requiring hospitalization (fatal, non-fatal), in patients randomized to degarelix versus leuprolide
- To assess the risk of death due to any cause in patients randomized to degarelix versus leuprolide
- To assess the rate of cardiovascular (CV)-related death in patients randomized to degarelix versus leuprolide

Prostate Cancer-Related Objectives

- To monitor testosterone levels at Day 28, 168 and 336 in the degarelix and leuprolide treatment groups
- To evaluate the progression-free survival (PFS) failure rates (defined as either death, radiographic disease progression^a, introduction of additional therapy related to prostate cancer^b or prostate-specific antigen [PSA] failure^c, whichever is first) in the degarelix and leuprolide treatment groups
 - a. One or more new metastatic skeletal lesions observed on bone scan; one or more new metastatic extraskeletal lesions at least 1.5 cm in greatest dimension visible on computed tomography or magnetic resonance imaging (MRI) scan as confirmed by the Investigator.
 - b. Additional therapy includes radiation, anti-androgens (except for initial symptomatic flare protection) and second-line treatment.
 - c. PSA failure is defined as an increase in serum PSA of 50%, and at least 5 ng/mL, compared to nadir, measured on two consecutive occasions at least 2 weeks a part.
- To compare the effects of degarelix with leuprolide with regards to local urinary tract and prostate cancer-related symptoms with the International Prostate Symptom Score (IPSS) questionnaire

Health Economics and Patient Reported Outcome (PRO) Objectives

• To compare the effects of degarelix with leuprolide with regards to healthcare resource use

Date: 24 Feb 2021 E-Statistical Analysis Plan-19595; Ver.7.0 Supersedes: 6.0 Page 11 of 51

- To compare the effects of degarelix with leuprolide with regards to health status through the EuroQol Group 5 Dimensions Questionnaire (EQ-5D-5L)
- To compare the effects of degarelix with leuprolide with regards to functional capacity and Quality of Life (QoL) through the Duke Activity Status Index (DASI)
- To compare the effects of degarelix with leuprolide with regards to heart-focused anxiety through the Cardiac Anxiety Questionnaire (CAQ)

Safety Objective

• To evaluate and compare the overall safety and tolerability of degarelix with leuprolide

2.1.3 Exploratory Objectives

• To compare the effects of degarelix with leuprolide with regards to a second confirmed (adjudicated) occurrence of the composite MACE endpoint, in the subgroup of patients that survived the first CV event

2.2 Endpoints

2.2.1 Primary Endpoint

• Time from randomization to the first confirmed (adjudicated) occurrence of the composite MACE endpoint

2.2.2 Secondary Endpoints

Key Secondary Endpoints

- Time from randomization to the first confirmed (adjudicated) occurrence of CV-related death, non-fatal myocardial infarction or non-fatal stroke
- Time from randomization to confirmed (adjudicated) CV-related death
- Time from randomization to the first confirmed (adjudicated) myocardial infarction

Other CV and Death-Related Endpoints

- Time from randomization to the first confirmed (adjudicated) stroke
- Time from randomization to the first confirmed (adjudicated) unstable angina requiring hospitalization
- Time from randomization to death due to any cause

Prostate Cancer-related Endpoints

Page 12 of 51

- Testosterone levels at Days 28, 168 and 336 in the degarelix and leuprolide treatment groups
- Time from randomization to failure in PFS
- Changes from baseline in IPSS Total and Qol scores

Health Economics and Patient-Reported Outcomes Endpoints

- Total number of CV-related hospitalization events over the duration of the trial
- Total number of coronary artery by-pass grafting (CABG) or percutaneous coronary intervention (PCI) procedures over the duration of the trial
- Total number of CV-related emergency room (ER) visit events over the duration of the trial
- Change in utility, based on EQ-5D-5L
- Changes from baseline in DASI Global score
- Changes from baseline in CAQ Global score and score per domain

Safety Endpoints

- Incidence and intensity of adverse events
- Changes in vital signs

